## 1. PROTOCOL SUMMARY

The following sections present an overview of the study, study schema, and Schedule of Activities (SoA). A list of abbreviations is presented in Section 10.4, Appendix 4.

### 1.1. Synopsis

**Protocol Title:** A Phase 2a, Double-Blind, Randomized, Placebo-Controlled, Multicenter Study to Assess the Safety of Engensis in Participants with Amyotrophic Lateral Sclerosis

**Short Title:** Phase 2a Study to Assess the Safety of Engensis in Amyotrophic Lateral Sclerosis

#### Rationale:

The purpose of this study is to evaluate the safety of intramuscular (IM) administration of Engensis in Participants with Amyotrophic Lateral Sclerosis (ALS) as compared to Placebo. Safety will be assessed by incidences of treatment-emergent adverse events (TEAEs), treatment-emergent serious adverse events (TESAEs), injection site reactions (ISRs) and other adverse events of special interest (AESIs), and the clinically significant laboratory values after injections for Engensis compared to Placebo. Exploratory endpoints include assessment of muscle function using the Revised Amyotrophic Lateral Sclerosis Functional Rating Scale (ALSFRS-R) and ALSFRS-R subscores for Fine and Gross Motor Function; muscle strength by quantitative testing using Handheld Dynamometry (HHD) and the Accurate Test of Limb Isometric Strength (ATLIS) where available; quality of life using the ALS Assessment Questionnaire (ALSAQ-40); patient global impression of change (PGIC), and clinical global impression of change (CGIC); and evaluation of lung function using Slow Vital Capacity (SVC). Muscle biopsies will be performed during the study for future biomarker analyses.

Engensis contains the active pharmaceutical ingredient VM202, a novel genomic complementary deoxyribonucleic acid (cDNA) hybrid human hepatocyte growth factor (HGF) coding sequence (HGF-X7) expressing two isoforms of HGF, HGF728 and HGF723, being developed for treatment of ALS.

Data from Helixmith's first clinical trial in ALS, the Phase 1/2 ALS study (VMALS-001), which included 18 Participants who were followed for 9 months, suggested that targeted delivery of HGF to motor neurons via intramuscular (IM) injections of Engensis was safe and well-tolerated. Safety assessments during the study included reports of 79 adverse events (AEs) in 17 Participants (94.4%), including 26 mild injection site reactions (Grade 1). Five SAEs were reported in 3 Participants. Only injection site reactions were considered related to study treatment. Following injections until Day 90, a plateau or a relative slowing in decline of the ALSFRS-R scores and muscle strength was noted, suggesting a slowing of disease progression. After 90 days, the plateau was no longer observed in the ALSFRS-R, with the notable exception of a trend toward better preservation of bulbar and breathing functions as measured by the ALSFRS-R.

---

Participants randomly assigned to Engensis will receive a total dose of 192 mg VM202 divided into 3 Treatment Cycles of 64 mg VM202 each. In this study, the per-injection amount (0.25 mg) of Engensis will be identical to that used in the Phase 1/2 ALS study and was also used in three diabetic peripheral neuropathy (DPN) studies, but the dosing schedule will differ. IM injections of Engensis or Placebo to muscles in hands, upper and lower arms, and legs will be divided into two Injection Visits scheduled two weeks apart during three Treatment Cycles: on Days 0 and 14 (Treatment Cycle 1), with retreatment on Days 60 and 74 (Treatment Cycle 2), and Days 120 and 134 (Treatment Cycle 3).

**Objectives and Endpoints**

Objectives	Endpoints
Primary 
 
To evaluate the safety of intramuscular (IM) injections of Engensis in Participants with Amyotrophic Lateral Sclerosis (ALS) compared to Placebo
 
	
 
Incidence of treatment-emergent adverse events (TEAEs) and treatment-emergent serious adverse events (TESAEs) for Engensis compared to Placebo
 
Incidence of injection site reactions for Engensis compared to Placebo
 
Incidence of clinically significant laboratory values for Engensis compared to Placebo
 

Exploratory 
 
To evaluate changes in muscle function following Engensis injections in ALS Participants compared to Placebo
 
	
 
Change from Baseline (Day 0) in total mean Revised Amyotrophic Lateral Sclerosis Function Rating (ALSFRS-R) scores at Day 180 for Engensis compared to Placebo
 
Change from Baseline (Day 0) in ALSFRS-R subscores for Fine and Gross Motor Functions (sum of scores for items 4 to 9) and for Bulbar Function (sum of scores for items 1 to 3) on Days 30, 60, 84, 120, 144, and 180 for Engensis compared to Placebo
 
Changes in the slope of the total ALSFRS-R score over time for Engensis compared to Placebo
 

 
To evaluate muscle strength changes following Engensis injections in ALS Participants compared to Placebo
 
	
 
Change from Baseline (Day 0) in muscle strength assessed bilaterally by Handheld Dynamometry (HHD) in muscles in the upper and lower extremities on Days 30, 60, 84, 120, 144, and 180 for Engensis compared to Placebo
 

Objectives	Endpoints
	
 
Change from Baseline (Day 0) in the Accurate Test of Limb Isometric Strength (ATLIS) where available at Days 30, 60, 84, 120, 144, and 180 for Engensis compared to Placebo
 

 
To evaluate Quality of Life improvement following Engensis injections in ALS Participants compared to Placebo
 
	
 
Change from Baseline (Day 0) in Quality of Life (QoL) using the ALS Assessment Questionnaire (ALSAQ; with 40 items, ALSAQ-40) on Days 84 and 180 for Engensis compared to Placebo
 


 
To evaluate Patient and Clinical Reported Outcome improvement following Engensis injections in ALS Participants compared to Placebo
 
	
 
Patient Global Impression of Change (PGIC) and Clinical Global Impression of Change (CGIC) at Days 84 and 180 for Engensis compared to Placebo
 

 
To determine whether IM administration of Engensis has effects on respiratory function in ALS Participants compared to Placebo
 
	
 
Change from Baseline (Day 0) in Slow Vital Capacity (SVC) on Days 30, 60, 84, 120, 144, and 180 for Engensis compared to Placebo
 
Time to tracheostomy for Engensis compared to Placebo
 

 
To determine whether IM administration of Engensis has positive effects on survival in ALS Participants compared to Placebo
 
	
 
Time to all-cause mortality by Day 180 for Engensis compared to Placebo
 

 
To determine whether IM administration of Engensis has positive effects on muscle atrophy in ALS Participants compared to Placebo
 
	
 
Change from Baseline (Day 0) in biomarkers for muscle atrophy in biopsies collected before and after injections for Engensis compared to Placebo
 

---

## Overall Design

VMALS-002-02 is a Phase 2a, double-blind, randomized, placebo-controlled, multicenter study designed to assess the safety of Engensis (containing the active pharmaceutical ingredient VM202) in Participants with ALS. Following the completion of the informed consent process, Screening activities (within 30 days prior to Day 0) will determine which Participants meet the eligibility criteria and who will be enrolled and randomly assigned in a double-blind fashion in a 2:1 ratio to either Engensis or Placebo, respectively.

During Screening, medical history, familial cancer history, demographics, vital signs, weight and height, complete physical examination, the ALSFRS-R, slow vital capacity (SVC), 12-lead electrocardiogram (ECG), laboratory assessments (coagulation profile, serum chemistry, and hematology), viral screening, a record of all concomitant medications and procedures, and urine pregnancy test for females of childbearing potential will be conducted. Adverse event (AE) assessment will start upon completion of the consent process at the start of Screening and treatment-emergent adverse event (TEAE) assessment, including injection site reactions, will start after the first injection of Engensis or Placebo (Day 0) and continue throughout the study.

Following randomization and prior to the first IM injections of Engensis or Placebo on Day 0, vital signs and weight, a complete physical examination, urine pregnancy test, SVC, concomitant medications and procedures, measurement of muscle strength by HHD and ATLIS (at clinical study sites where available), ALSFRS-R, muscle biopsy, and the quality of life assessment with the ALSAQ-40 will be completed.

All Participants will receive 0.5-mL (0.25 mg) IM injections (2 to 20 injections per muscle, depending on the anatomical location of the muscle) of Engensis or Placebo in target muscles at each of two dosing Visits during 3 Treatment Cycles: Treatment Cycle 1 on Days 0 and 14, Treatment Cycle 2 on Days 60 and 74, and Treatment Cycle 3 on Days 120 and 134. Vital sign measurements will be performed at 2 hours after completion of IM injections of Engensis or Placebo on Days 0, 14, 60, 74, 120, and 134.

Vital signs will be recorded at all Study Visits. On Day 0, a blood sample will be collected for future genetic testing. Muscle biopsies will be collected on Day 0, 84 (optional), and 144.

All Participants will receive 256 IM injections per Treatment Cycle (128 injections on each of 2 dosing days) as a divided dose to multiple injection sites in each muscle identified in the upper extremities (hands: first dorsal interosseous, abductor pollicis brevis; arms: biceps, deltoid, extensor carpi radialis, flexor carpi ulnaris, and flexor carpi radialis) and lower extremities (legs: quadriceps, gastrocnemius, and tibialis anterior). Each injection contains 0.25 mg Engensis/0.5 mL or 0.5 mL of Placebo. Participants assigned to Engensis will receive a total dose of 192 mg (3 cycles at 64 mg each) during the study.

Follow-up Study Visits will be conducted on Days 30, 84, 144, and 180 or early termination (ET). At the Day 180/ET Visit, the following assessments will be conducted: vital signs and weight, complete physical examination, 12-lead ECG, urine pregnancy test, ALSFRS-R, SVC, HHD and ATLIS (at sites where available), ALSAQ-40, PGIC, CGIC, concomitant medications, and TEAEs. Blood will be drawn for serum chemistry and hematology.

---

**Study and Treatment Duration:**

Screening will occur up to 30 days prior to Baseline (Day 0) and Participants will be followed from Day 0, the day of first Study Injections, to Day 180/ET.

**Visit Frequency:**

Consented Participants will be seen and evaluated for enrollment during Screening (up to 30 days prior to Baseline, Day 0). There are 10 Visits during the study from Day 0 to Day 180 for Study Injections and follow-up.

**Intervention Groups and Duration:**

Two treatment groups of Participants (Engensis or Placebo) will be in the study for 180 days.

**Number of Participants (N = 18):**

[figure not shown]
The target sample size is 18 Participants who will be randomized in a 2:1 ratio to Engensis or Placebo (12:6).

**Data Safety Monitoring Board:**

The independent Data Safety Monitoring Board (DSMB) will periodically review, first on a limited set of noncomparative (blinded) tables and/or listings of all data and, if there is a concern, a comparative (unblinded) analysis will be conducted, including review of all reported TEAEs and TESAEs. The DSMB may perform multiple noncomparative analyses for safety. Comparative information will not be shared with the Sponsor or the Project Steering Committee, except in the event that the DSMB recommends a temporary suspension or termination of the study.

---

**1.2. Study Schema**

### 1.3. Schedule of Activities (SoA)

Study Day:	Screen-ing Days -30 to -1	Treatment Cycle 1				Treatment Cycle 2				Treatment Cycle 3				End of Study/ ET	
		1 st Injections		2 nd Injections		3 rd Injections		4 th Injections		5 th Injections		6 th Injections			
		Day 0 a		Day 14 b		Day 30		Day 60		Day 84		Day 120		Day 134 b	
Visit Window (days):				± 1		± 3		± 3		± 1		± 3		± 1	
Procedure		pre-dose	post-dose	pre-dose	post-dose										
1 Informed Consent	X														
2 Demographics, Baseline Characteristics	X														
3 Medical History and Familial Cancer History	X														
4 Vital Signs, Weight, Height	X	X	X	X	X	X	X	X	X	X	X	X	X	X	X
5 Complete Physical Examination	X	X		X		X	X		X	X	X		X		X
6 12-Lead ECG	X									X					X
7 Coagulation Profile	X														
8 Serum Chemistry, Hematology	X					X					X				X
9 Blood Sample for Future Genetic Testing		X													
10 Viral Screening	X														
11 Urine Pregnancy Test	X	X													X
12 SVC	X	X				X	X			X	X				X
13 Concomitant Medications and Procedures	X	X		X		X	X		X	X	X		X		X

Study Day:	Screen -ing Days -30 to -1	Treatment Cycle 1				Day 30	Treatment Cycle 2				Day 84	Treatment Cycle 3				End of Study/ ET Day 144			
		1 st Injections		2 nd Injections			3 rd Injections		4 th Injections			5 th Injections		6 th Injections					
		Day 0 a		Day 14 b			Day 60		Day 74 b			Day 120		Day 134 b					
Visit Window (days):				± 1		± 3	± 3		± 1		± 3	± 3		± 1		± 3      ± 7			
Procedure		pre-dose	post-dose	pre-dose	post-dose		pre-dose	post-dose	pre-dose	post-dose		pre-dose	post-dose	pre-dose	post-dose				
14	Randomization	X																	
15	Study Injections		X		X			X		X			X		X				
16	ALSFRS-R	X	X			X	X				X	X				X      X			
17	HHD		X			X	X				X	X				X      X			
18	ATLIS		X			X	X				X	X				X      X			
19	ALSAQ-40		X								X					X			
20	PGIC and CGIC										X					X			
21	Muscle Biopsy c		X								X d					X			
22	AEs, TEAEs, SAEs, TESAEs	X (AEs)						TEAEs											
23	AESIs																		
24	AESI: Injection Site Reactions		X		X		X		X		X		X		X				

---

**FOOTNOTES FOR THE SCHEDULE OF ACTIVITIES**

**Note:** The Schedule of Activities includes activities during Screening and all Study Visits.

**Order of Assessments during Visits (if assessment is to be performed):** AEs/TEAEs, vital signs and weight, ALSFRS-R, HHD, ATLIS, pregnancy test, complete physical exam, SVC, ALSAQ-40, other questionnaires (PGIC and CGIC), blood sample collection for laboratory assessments, and muscle biopsy

- a Day 0 is the Baseline Visit
- b The Day 14 Visit will be scheduled 13-15 days after the Day 0 Visit, the Day 74 Visit will be scheduled 13-15 days after the Day 60 Visit, and the Day 134 Visit will be scheduled 13-15 days after the Day 120 Visit
- c Muscle biopsies will be collected as the last procedure of the Visit. It is collected predose on Day 0.
- d Day 84 muscle biopsy is optional.

**Abbreviations:** AEs = adverse events; AESI = adverse events of special interest; ALSFRS-R = Revised Amyotrophic Lateral Sclerosis Functional Rating Scale; ALSAQ-40 = Amyotrophic Lateral Sclerosis Assessment Questionnaire, 40 questions; ATLIS = accurate test of limb isometric strength; CGIC = Clinical Global Impression of Change; D = day; ET = early termination or withdrawal; HHD = Handheld Dynamometry; PGIC = Patient Global Impression of Change; SVC = Slow Vital Capacity; TEAEs = treatment-emergent adverse events; TESAEs = treatment-emergent serious adverse events

1. **Informed Consent** process is to be completed at Screening prior to conducting any study-specific procedures.
2. **Demographics and Baseline Characteristics** will include age, gender, race, and ethnicity and will be collected at Screening.
3. **Medical History and Familial Cancer History:** A medical history and familial cancer history will be obtained at Screening. The Investigator will confirm the diagnosis of ALS using the revised El Escorial / Airlie House diagnostic criteria. Participants will be confirmed as having clinically definite ALS, clinically probable ALS, or clinically probable laboratory-supported ALS  $\leq 4$  years.
4. **Vital Signs, Weight, and Height:** Vital signs will be measured at Screening, predose, and 2 hours ( $\pm 1$  hour) post-dose at Study Injection Visits during the Treatment Cycle 1 (Days 0 and 14), Treatment Cycle 2 (Days 60 and 74), and Treatment Cycle 3 (Days 120 and 134). Vital signs will also be measured at Study Visits on Days 30, 84, 144, and 180/ET (Day 180 or Early Termination). After the Participant has rested in the seated position for 5 minutes, vital signs will be collected, including temperature, sitting blood pressure, heart rate, respiratory rate, and oxygen saturation on room air. The method of temperature measurement should be according to the Site's policy and should be consistently applied. Weight will be collected at Screening and predose at Study Injection Visits (Days 0, 14, 60, 74, 120, and 134); height will only be measured at Screening.
5. **Complete Physical Examination** will be performed at Screening, predose on Days 0, 14, 60, 74, 120, and 134, and at Study Visits on Days 30, 84, 144, and 180/ET. The examination will include the following: head, eyes, ears, nose, and throat (HEENT); heart; lungs; abdomen; extremities; lymph nodes; neurological; musculoskeletal system; and skin/integumentary systems. Any abnormalities should be categorized as clinically significant (CS) or not clinically significant (NCS), and the abnormalities should be recorded as adverse events, except at Screening.
6. **12-Lead Electrocardiogram (ECG)** will be performed at Screening, Day 84, and Day 180/ET. Any clinically significant findings at Screening will be recorded as part of the medical history. Clinically significant abnormalities are to be recorded as adverse events, except at Screening. The ECG recording must be stored with the Participant's records.
7. **Coagulation Profile** will be evaluated at Screening and will include prothrombin time (PT), partial prothrombin time (PTT), and International Normalized Ratio (INR).

---

**8. Serum Chemistry and Hematology:** Laboratory assessments will be evaluated at Screening (to establish eligibility) and on Days 60, 120, and 180/ET.

**Chemistry** includes sodium, potassium, chloride, bicarbonate, calcium, inorganic phosphate, magnesium, glucose, amylase, lipase, creatine kinase, lactate dehydrogenase, and:

- a. Kidney function tests (blood urea nitrogen, creatinine)
- b. Liver function tests (aspartate aminotransferase [AST], alanine aminotransferase [ALT], alkaline phosphatase, gamma-glutamyl transpeptidase [GGT], total bilirubin, total protein, and albumin)

**Hematology** includes platelet count, hemoglobin, hematocrit, white blood cell count, and neutrophil count

**9. Blood Sample for Future Genetic Testing:** A blood sample will be collected at predose on Day 0 and stored.

**10. Viral Screening** is to be conducted at Screening and includes tests for human immunodeficiency virus (HTV), human T cell lymphotropic virus (HTLV) I/II antibody with reflex confirmatory assay, hepatitis B virus (HBV: IgM HBcAb, HBsAb, and HBsAg, and a quantitative HBV if needed clinically), and anti-hepatitis C virus (HCV) antibodies and a positive qualitative PCR if needed clinically. Testing will be performed at a local laboratory. All tests for HIV, HTLV, HBV, and HCV must be completed and negative prior to randomization.

**11. Urine Pregnancy Test:** Women of childbearing potential must have a negative urine pregnancy test at Screening, predose at Study Injection Visit on Day 0 and Day180/ET.

**12. Slow Vital Capacity (SVC)** will be measured at Screening, predose on Days 0, 60, and 120, and at Study Visits on Days 30, 84, 144, and 180/ET.

**13. Concomitant Medications and Procedures:** Record all medications or vaccines, including over-the-counter or prescription medicines, vitamins, herbal supplements, and procedures that the Participant was receiving during the 30 days prior to completion of the informed consent process at Screening, predose at Study Injection Visits on Days 0, 14, 60, 74, 120, and 134, and at Study Visits on Days 30, 84, 144, and 180/ET. For each medication, treatment, or procedure, the following information will be collected: Medication trade or generic name, type of procedure, indication, start date, stop date or ongoing, dose, units, frequency, and route.

**14. Randomization:** Completion of Screening activities, randomization, and first Study Injections (Treatment Cycle 1, Day 0) will occur on the same day (Day 0).

**15. Study Injections:** IM injections of Engensis or Placebo will be administered during Treatment Cycle 1 (1st and 2nd Study Injections on Days 0 and 14), Treatment Cycle 2 (3rd and 4th Study Injections on Days 60 and 74), and Treatment Cycle 3 (5th and 6th Study Injections on Days 120 and 134).

**16. Revised Amyotrophic Lateral Sclerosis Functional Rating Scale (ALSFRS-R)** will be performed at the Clinical Site at Screening, predose on the Days 0, 60, and 120, and on Days 30, 84, 144, and 180/ET.

**17. Handheld Dynamometry (HHD)** will be measured at the Clinical Site predose on Days 0, 60, and 120, and at Visits on Days 30, 84, 144, and 180/ET.

**18. ATLIS** will be measured (only at sites that have the ATLIS equipment) predose on Days 0, 60, and 120, and at Visits on Days 30, 84, 144, and 180/ET.

**19. Amyotrophic Lateral Sclerosis Assessment Questionnaire, 40 questions (ALSAQ-40)** will be measured predose on Day 0 and at Visits on Days 84 and 180/ET.

**20. Patient Global Impression of Change (PGIC) and Clinical Global Impression of Change (CGIC)** will be conducted at Visits on Days 84 and 180/ET.

**21. Muscle Biopsy:** Biopsies of the gastrocnemius muscle around the injection sites will be collected and stored at Day 0 predose, and Days 84 (optional) and 144 (approximately10 days after the second day of injections of Treatment Cycles 2 and 3).

---

22. **Adverse Events (AEs), Treatment-Emergent Adverse Events (TEAEs), Serious Adverse Events (SAEs) and Treatment-Emergent Serious Adverse Events (TESAEs):** AEs will be recorded after informed consent until the first injections on Day 0. After the start of the 1st Injections on Day 0 through Day 180, AEs will be recorded as treatment-emergent adverse events (TEAEs). Treatment-emergent serious adverse events (TESAEs) occurring after randomization and throughout the study will be recorded. SAEs occurring after the completion of the consent process and before the 1st Injections on Day 0 should be recorded and reported as SAEs only if associated with a protocol-specified procedure. All SAEs, and TESAEs occurring after the time of the 1st Injections through the last Study Visit on Day 180, should be recorded and reported to the Sponsor/designee within 24 hours of awareness of the SAE/TESAE by the Site.

23. **Adverse Events of Special Interest (AESIs):** All AESIs will be continuously monitored throughout the study.

24. **AESI: Injection Site Reactions (ISRs)** must be initially assessed immediately after all injections at an Injection Visit. The Investigator or designee will follow up with the Participant within 2 to 3 days after Study Injections to ask the Participant about reactions at any injection sites and, if any are noted, the worst reaction will be recorded as a TEAE and considered an AESI.

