### 5.1. Inclusion Criteria

1. Male or female Participants age  $\geq$  18 years, but  $\leq$  80 years, at time of completion of the informed consent process
2. Clinically definite or probable Amyotrophic Lateral Sclerosis (ALS) or laboratory-supported probable ALS as defined in the revised El Escorial/Airlie House diagnostic criteria
3. The site of onset of ALS symptoms is a limb and experiencing symptoms of lower motor dysfunction (e.g., weakness, atrophy, cramps, poor circulation, etc.) with upper motor neuron symptoms (e.g., brisk reflexes, spasticity)
4. Onset of ALS symptoms  $\leq$  4 years
5. Slow Vital Capacity (SVC)  $\geq$  50% of predicted value at Screening
6. Not taking riluzole, or on a stable dose (defined as no noted toxicities) for at least 30 days prior to Screening and throughout the study
7. Not taking edaravone or on a maintenance cycle for at least 30 days prior to Screening and throughout the study
8. For females of childbearing potential, a negative urine pregnancy test at Screening and on Day 0
9. Male Participants and their female partners must agree to use double-barrier contraception during the study or provide proof of postmenopausal state (minimum 1 year) or surgical sterility
10. Male Participants must not donate sperm during the study
11. Female Participants must be nonpregnant, nonlactating, and either postmenopausal for at least 1 year, or surgically sterile for at least 3 months, or agree to use double-barrier contraception from 28 days prior to randomization (Day 0) and/or their last confirmed menstrual period prior to study randomization (whichever is longer) until the end of the study
12. Capable of complying and willing to comply with the requirements and restrictions in the informed consent form and this protocol
13. Willing to forgo new experimental ALS treatments for at least 6 months following randomization

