## 8.2. Safety Assessments

### 8.2.1. Physical Examinations

A complete physical examination (PE) will be performed at the Screening, predose on Days 0, 14, 60, 74, 120, and 134, and on Days 30, 84, 144, and Day 180/ET. The complete PE will include the following: an examination of the skin/integumentary systems, general appearance, head, neck (including thyroid), eyes, ears, nose, throat, lymph nodes, chest (lungs), heart, abdomen, musculoskeletal system, neurological system, and any additional assessments needed to establish Baseline status or evaluate symptoms or AEs. Height will be recorded only during Screening. Any abnormalities should be categorized as clinically significant (CS) or not clinically significant (NCS), and the abnormalities recorded.

The Investigator or qualified medical personnel who routinely perform these evaluations in patients with ALS will conduct the examination, determine findings, and assess any abnormalities as to clinical significance.

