**Events Meeting the AE Definition**

- Any abnormal laboratory test results (hematology, or clinical chemistry) or other safety assessments (e.g., ECG, radiological scans, vital signs measurements), including those that worsen from Baseline, considered clinically significant in the medical and scientific judgment of the investigator (i.e., not related to progression of underlying disease).
- Exacerbation of a chronic or intermittent pre-existing condition including either an increase in frequency and/or intensity of the condition.
- New conditions detected or diagnosed after study intervention administration even though it may have been present before the start of the study.
- Signs, symptoms, or the clinical sequelae of a suspected drug-drug interaction.
- Signs, symptoms, or the clinical sequelae of a suspected overdose of either study intervention or a concomitant medication. Overdose per se will not be reported as an AE/SAE unless it is an intentional overdose taken with possible suicidal/self-harming intent. Such overdoses should be reported regardless of sequelae.

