**Events NOT Meeting the AE Definition**

- Any clinically significant abnormal laboratory findings or other abnormal safety assessments that are associated with the underlying disease, unless judged by the Investigator to be more severe than expected for the Participant's condition.
- The disease/disorder being studied or expected progression, signs, or symptoms of the disease/disorder being studied, unless more severe than expected for the Participant's condition.
- Medical or surgical procedure (e.g., endoscopy, appendectomy): the condition that leads to the procedure is the AE.
- Situations in which an untoward medical occurrence did not occur (social and/or convenience admission to a hospital).

- Anticipated day-to-day fluctuations of pre-existing disease(s) or condition(s) present or detected at the start of the study that do not worsen.

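### Schedule of Activities footnote 5 records physical-examination abnormalities as adverse events without a clinical-significance limit, contrary to Section 8.2.1 and Appendix 2, so TEAE counts may be inflated and recorded differently between sites

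*Protocol*

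**What the plan says.** The protocol states the rule for examination findings in several places, and the statements differ.

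- **Section 1.3, footnote 5 (physical examination).** Every abnormality is rated clinically significant (CS) or not (NCS), "and the abnormalities should be recorded as adverse events, except at Screening". The sentence is not limited to CS findings, nor to new or worsened ones.
- **Section 1.3, footnote 6 (ECG).** "Clinically significant abnormalities are to be recorded as adverse events, except at Screening".
- **Section 8.2.1.** "Any abnormalities should be categorized as clinically significant (CS) or not clinically significant (NCS), and the abnormalities recorded". Adverse events are not mentioned.
- **Appendix 2, Section 10.2.1, events that are AEs.** An abnormal laboratory result or other safety assessment is listed if it is "considered clinically significant in the medical and scientific judgment of the investigator", with a gloss that this means unrelated to progression of the underlying disease.
- **Appendix 2, Section 10.2.1, events that are not AEs.** "The disease/disorder being studied or expected progression, signs, or symptoms of the disease/disorder being studied", unless more severe than expected. Pre-existing conditions that fluctuate but do not worsen are also listed.
- **Section 10.2.2 and SAP 6.14.1.** A TEAE must have been absent before treatment or have worsened.
- **Section 8.5.9.** All disease-related events qualify as AEs except a short list of ALS symptoms. The list omits weakness, atrophy and spasticity.

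Section 9.3.1 puts TEAE incidence in the first-listed primary endpoint and plans no formal safety test. SAP 6.14.5 has a separate Normal/NCS/CS shift table for the examination (Table 14.3.6.3).

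**The concern.** For an NCS finding, or a sign that simply reflects expected progression, a site cannot follow both footnote 5 and Appendix 2. The footnote makes it an adverse event and the appendix does not. Section 8 allows no protocol waivers, so each site must choose which text governs.

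Such findings should be common. Inclusion criterion 3 requires participants to be "experiencing symptoms of lower motor dysfunction (e.g., weakness, atrophy, cramps, poor circulation, etc.) with upper motor neuron symptoms", the disease is progressive, and the earlier ALS study saw strength decline steadily after three months (Section 2.1). New or worse neurological and musculoskeletal findings are to be expected over 180 days in both arms.

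Two outputs are exposed: the any-TEAE proportion and the tables by system organ class and preferred term. Because no test is planned, the safety conclusion rests on reading these descriptive counts. If they depend partly on which section a site followed, a difference between arms can appear or disappear for reasons unrelated to the product.

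**Working it through.** **1. How each type of post-Screening finding is classified**

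| Finding | Footnote 5 | Appendix 2, Section 10.2.1 | Meets the absent-or-worsened TEAE test? |
|---|---|---|---|
| ALS sign unchanged since before treatment | AE | Not an AE | No |
| New or worsened, NCS, not disease-related | AE | Not listed as an AE (CS required) | Yes |
| New or worsened, expected ALS progression | AE | Not an AE | Yes |
| New or worsened, CS, not disease-related | AE | AE | Yes |

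Only the second and third rows change the TEAE count. The first is stopped by the TEAE definition even if a site logs it as an AE.

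**2. Opportunities.** Examinations after the first injection fall on Days 14, 30, 60, 74, 84, 120, 134, 144 and 180/ET, so there are 9.

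**3. Weight of one participant.** Section 5.3 gives 18 participants, 12:6. One placebo participant is 1/6 = 16.7 points. One Engensis participant is 1/12 = 8.3 points.

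**4. Existing level of any-event incidence.** The only any-AE rate in ALS that the documents give is 17 of 18 in the earlier study (Section 1.1).

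- 17/18 = 94.4%, as stated; exact 95% CI 72.7% to 99.9%.
- Headroom to 100%: 1 − 17/18 = 5.6 points.
- Chance that all 18 participants have an event at that rate, with no contribution from footnote 5: (17/18)^18 = 0.36. Over the confidence interval this runs from 0.003 to 0.975.

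**5. Possible inflation (assumed inputs).** The documents give no rate for recorded NCS findings. Let q be the chance per examination of recording one, with examinations independent. The chance of at least one over nine is 1 − (1 − q)^9. With base rate b, any-TEAE incidence becomes 1 − (1 − b)(1 − q)^9.

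| q (assumed) | At least one NCS finding | Incidence if b = 50% (assumed) | Incidence if b = 94.4% |
|---|---|---|---|
| 0.05 | 37% | 69% | 96.5% |
| 0.10 | 61% | 81% | 97.8% |
| 0.20 | 87% | 93% | 99.3% |
| 0.30 | 96% | 98% | 99.8% |

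Inflation is large if the underlying rate is moderate. It cannot exceed 5.6 points if the rate is already near that of the earlier study. The documents do not say which case applies.

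**The case against.** **Appendix 2 may not exclude NCS findings.** Its entry on abnormal assessments is one item in a list and does not say that only significant findings count. The general definition in Section 10.2.1 covers any unfavorable, unintended sign, and broad capture can be deliberate in a small safety study. This stands in part. The conflict is plainest for expected-progression findings, which Appendix 2 excludes expressly. For other NCS findings, the significance condition on abnormal safety assessments would do no work if non-significant ones were AEs as well. Physical examination is itself placed under Safety Assessments (Section 8.2). If broad capture is intended, Section 8.2.1 and Appendix 2 need changing instead.

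**Stable ALS signs.** A reader might infer that every entrant's existing ALS signs become TEAEs. The documents do not support this: Appendix 2 excludes expected disease signs and unworsened conditions, and both TEAE definitions require absence before treatment or worsening.

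**The Day 0 predose examination.** A reader might also infer that its findings count because SAP 6.14.1 works by day. That rule still requires the event to have emerged or worsened. Section 8.5.1 and SAP 6.14.1 start TEAE collection after the first injections and send earlier occurrences unrelated to study procedures to medical history. What remains is a data-handling risk: SAP 6.2.5 imputes a missing start date of an ongoing event to the first dose, but SAP 6.2.4 drops the imputation where other eCRF data contradict it.

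**Other outputs separate these findings.** Largely true. The severity and relatedness tables help, although SAP 6.14.1 treats missing severity as maximum and missing relationship as related.

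**Conclusion.** The inconsistency is real and should be corrected. Footnote 5 sets a recording rule for data behind the first-listed primary endpoint, and the rule contradicts Section 8.2.1 and the protocol's own AE definition. It bears on new or worsened NCS findings and expected-progression findings at nine post-injection examinations. Any-TEAE incidence and the tables by system organ class and preferred term may be inflated and recorded unevenly between sites.

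Each participant whose any-TEAE status depends on the reading moves the placebo percentage by 16.7 points or the Engensis percentage by 8.3. How many there would be cannot be computed, and the table by q rests on assumed inputs.

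It would be tempting to conclude that footnote 5 drives TEAE incidence to 100% in both arms and removes the contrast. The documents do not show that. Incidence may be near ceiling without the footnote, as 17 of 18 in the earlier study suggests. That figure is from an open-label study followed for nine months, and its recording rule for examination findings is not given. TESAEs, injection site reactions and clinically significant laboratory values are not directly affected, and no test or power calculation is involved.

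**What to change.** Use the same sentence in footnote 5 and Section 8.2.1, for example: *After Screening, an examination abnormality is recorded as an adverse event only if it meets Section 10.2.1, that is, if it is clinically significant, new or worse than before treatment, and not an expected sign of ALS; every other abnormality is kept on the examination eCRF.* Keep the existing allowance in Appendix 2 for disease signs more severe than expected.

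In the same edit, reconcile Section 8.5.9 with the Appendix 2 exclusion list on which ALS signs are not AEs, and check both against Section 8.5.4.2, which makes progressive muscle weakness an AESI. Otherwise sites still lack a single rule for weakness and atrophy.

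The cost is a short amendment and a site memo, with no new data collection. The downside is fewer NCS findings in the TEAE tables. They remain in shift Table 14.3.6.3 and Listing 16.2.8.6. Because SAP 6.2.14 keeps unscheduled, repeat and early-termination assessments out of tables, NCS findings from those examinations would appear in the listing only.
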